Appendix 3. Definition and Use of Visit Windows in Reporting

Statistical analyses for full analysis set will be based on time intervals that are constructed according to the duration of treatment. The planned time interval definitions are summarized below.

Scheduled Visit number	Time interval (label)	Time interval (days)	Target time point (day)
1	Screening ¹	[-52, -46]	-49
2	Baseline ²	[-7, 0]	0
3	Week 2	[11, 17]	14
4	Week 4	[25, 31]	28
5	Month 3	[84, 98]	91
6	Month 6	[168, 196]	182
7	Month 9	[266, 280]	273
8	Month 12	[351, 379]	365
9	Follow-up	[373, 385]	379

1. Screening visit will take place during the Week 19 Visit for study A8241021.

2. Assessment results collected at Week 26 for Study A8241021 will be used for Baseline Day 1 (V2).

If data obtained from the multiple visits are included in the same interval, the one closest to the target date in that time interval will be used for analysis. If two visits are equally distant from the target date, then the later one will be used.

The study day associated with a given date will be calculated as: (date of interest) – (first dosing date) + 1. Consequently, Day 0 indicates the day before Day 1, the first dosing date in the study.

The baseline reference period for assessing treatment emergent adverse events (TEAEs) will be the period prior to Day 1.

The frequency distribution of study days for each visit will be reviewed by clinician to expand visit windows for the analyses, if necessary, before locking and unblinding the database.

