6.3. Laboratory Safety Tests

Safety laboratory tests will be performed as described in the protocol.

To determine if there are any clinically significant laboratory abnormalities, the haematological, clinical chemistry (serum) and urinalysis safety tests will be assessed against the criteria specified in the sponsor reporting standards. The assessment will take into account whether each subject's test result is within or outside the laboratory reference range for the particular laboratory parameter.

Assessment results collected at Week 26 for Study A8241021 will be used for Baseline Day 1.

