8.2. Statistical Analyses

8.2.1. Analysis of Secondary Endpoints

The efficacy variables are:

- Change from baseline in the Total Motor Score (TMS) assessment of the Unified Huntington Disease Rating Scale (UHDRS) after 6 and 12 months of treatment.
- Change from baseline in the Total Maximum Chorea (TMC) score of the UHDRS after 6 and 12 months of treatment.

- Clinical Global Impression-Improvement score after 6 and 12 months of treatment.

[figure not shown]
Descriptive statistics (n, mean, standard deviation, median, minimum and maximum) and 90% confidence interval will be provided to summarize results for each visit. The baseline and change from baseline values will be summarized as well by visit. A two-sided, paired *t*-tests at the 10% level of significance will also be used to summarize results. The paired *t*-tests will be done on all subjects and on three different groups. Baseline is defined as the final visit (Week 26) in the preceding double-blind study A8241021.

Clinical Global Impression-Improvement score after 6 and 12 months of treatment will be evaluated with descriptive statistics that includes n, mean, standard deviation (SD), median, minimum, and maximum. A two-sided, one-sample *t*-tests at the 5% level of significance will be applied to evaluate results.

Plots will be generated for mean change from baseline as well as mean over time as described in [Section 8.1](#).

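### Do the Baseline and Month 12 windows in SAP Appendix 3 misplace visits in a way that changes a result?

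*SAP*

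**What the plan says.** SAP Appendix 3 computes study day as the date minus the first dosing date, plus one. It then states: "Consequently, Day 0 indicates the day before Day 1, the first dosing date in the study". The rows that matter here are:

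| Row | Window (days) | Target |
|---|---|---|
| Screening | [-52, -46] | -49 |
| Baseline | [-7, 0] | 0 |
| Week 2 | [11, 17] | 14 |
| Month 12 | [351, 379] | 365 |
| Follow-up | [373, 385] | 379 |

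On scope, the appendix says: "Statistical analyses for full analysis set will be based on time intervals that are constructed according to the duration of treatment". There are two selection rules. The first begins "If data obtained from the multiple visits are included in the same interval, the one closest to the target date in that time interval" and takes that record. The second settles ties: "If two visits are equally distant from the target date, then the later one will be used".

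Baseline is also defined without any window. SAP 6.3 says "Assessment results collected at Week 26 for Study A8241021 will be used for Baseline Day 1", and footnote 2 of the Appendix 3 table repeats it. SAP 8.2.1 says "Baseline is defined as the final visit (Week 26) in the preceding double-blind study A8241021". SAP 8.3.9 takes the vital-signs baseline from the pre-dose readings at V2 on Day 1.

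The protocol places V8 on Day 365 ± 7 (section 6.2.7) and V9 on Days 372 to 379 (section 6.3). Footnote 5 of the Schedule of Activities puts V9 7 to 14 days after the last dose.

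**The concern.** Read literally, the appendix contradicts itself twice.

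First, a programmer who assigned baseline by window would find no baseline record for a subject dosed on the V2 date. Every change from baseline would be missing for that subject, and TMS and TMC are analysed as changes from baseline.

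Second, every protocol day for Follow-up lies inside the Month 12 window. The selection rules choose between several visits in one interval. They do not say which interval owns a single visit that fits two. WBC and ANC at each visit are listed among the primary endpoints in SAP 6.1, and blood is drawn for them at both V8 and V9. V9 comes after treatment has stopped, so a V9 count filed as Month 12 would mix an off-drug value into an on-drug summary of the safety signal that the study monitors most closely.

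**Working it through.** **Baseline day.** Study day = (date − first dosing date) + 1.

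- V2 on the first dosing date: 0 + 1 = Day 1. Baseline ends at Day 0 and Week 2 opens at Day 11, so Day 1 is in no window.
- V2 on the day before the first dose: −1 + 1 = Day 0. This reproduces the table's target.

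SAP 8.3.9 and Protocol 5.1 (Table 3, dosing from Day 1) describe the first case.

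**Screening.** The footnote says "Screening visit will take place during the Week 19 Visit for study A8241021". Week 19 is (26 − 19) × 7 = 49 days before Week 26. If V2 is the first dosing date, this is −49 + 1 = Day −48, against a target of −49. Day −48 is still inside [-52, -46].

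**Later rows.** Protocol Week 2 is Day 14 ± 3, which is Days 11 to 17 and equals the SAP window. The one-day slip is therefore confined to the Screening and Baseline rows.

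**Does the slip reach an estimate?** Footnote 2 and SAP 6.3, 8.2.1 and 8.3.9 all identify baseline by visit, and none of them uses the window. Appendix 3 also has the study-day distribution for each visit reviewed before lock, with windows widened if needed. Baselines sitting at Day 1 would be plain in that review.

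**Overlap.**

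- Protocol Follow-up days: 379 − 372 + 1 = 8. All 8 lie in [351, 379].
- Days in both windows: 373 to 379, which is 7.
- Day 372 is in Month 12 only.

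**When would V9 displace V8 at Month 12?** It must be at least as close to Day 365, because ties go to the later visit. Take the last dose to be on the V8 date, V8 on Days 358 to 372, V9 on Days 372 to 379, and a gap of 7 to 14 days.

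- Each of the 8 V9 days admits 8 V8 days (V9 − 14 to V9 − 7), so there are 8 × 8 = 64 date pairs.
- V8 is at most 7 days from Day 365. V9 on Day 373 or later is at least 8 days away and cannot win.
- V9 on Day 372 is 7 days away. It needs V8 to be 7 days away too, and the 7-day minimum gap leaves only V8 on Day 358 (gap 14). This is a tie, which V9 takes.
- Result: 1 of 64 pairs. This counts calendar combinations, not subjects.

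If V8 is missing, any V9 on Days 372 to 379 qualifies for Month 12, and on 7 of those 8 days it qualifies for Follow-up as well.

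**Which analyses could feel this?** Under SAP 5.1 and 8.1 the full analysis set serves efficacy, and safety uses the separate safety set. The V9 procedures in Protocol 6.3 include no TMS or CGI-I, and TMC is derived from TMS. C-SSRS is collected at V9, but SAP 8.3.6 summarises it as pre-dose against post-dose and at any time after baseline, so the Month 12/Follow-up boundary does not enter. WBC and ANC remain. SAP 8.3.7 sends laboratory summaries to the sponsor's reporting standards and does not mention Appendix 3.

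**The case for a change.** The strongest contrary argument is that the scope of Appendix 3 is not as clean as its first sentence suggests. No named efficacy endpoint is measured at V9, so a Follow-up row seems to have a purpose only for safety data. The appendix also defines the reference period for treatment-emergent adverse events, which is a safety matter. If the windows do govern laboratory summaries, the missing-V8 route may be less rare than it sounds. SAP 8.1 removes early-termination visits on and after 16 December 2016 from the summaries but says nothing of Follow-up visits, and SAP 2.1 asks subjects who stop early to attend Follow-up where possible. Such a subject could have V9 as the only Month 12 candidate. The 1 in 64 also depends on the fixed Day 372 to 379 range. Under the 7-to-14-day gap alone, V9 wins in 20 of 15 × 8 = 120 pairs.

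Part of this stands. The appendix should have stated its scope without ambiguity, and the pre-lock review can widen windows but cannot remove an overlap. The inference from the Follow-up row is weak, though. The table lists every scheduled visit, and Screening is there too although no TMS is taken at it. Of the 20 looser pairs, 19 put V9 before Day 372, outside the range in Protocol 6.3. The early-termination route still needs the unstated premise about laboratory data, and the documents give no count of such subjects.

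**Conclusion.** The inconsistencies are genuine but clerical, and no change to the plan follows.

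- **Baseline.** The row is one day off the appendix's own numbering. Four other statements fix baseline by visit, so the effect on estimates is nil.
- **Overlap.** Within the stated scope it touches no named efficacy endpoint, so the effect is again nil. Outside that scope, its only identified route to a result is WBC/ANC by visit. There the displacement count is 1 of 64 date pairs when both visits are on time, and of unknown frequency when V8 is missing.

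V8 and V9 are separately numbered visits with their own procedure lists. An analyst preparing a haematology table would ordinarily keep a record labelled Follow-up out of the Month 12 column, so the missing rule is a gap that gets filled sensibly. Rewriting the table would bring no demonstrable gain in any planned analysis.

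This rests on three assumptions: baseline is mapped by visit, as the SAP says repeatedly; the full-analysis-set scope means what it states; and the sponsor's laboratory standards, which are not in the documents, do not import these windows. If the last were false, the exposure would be a misplaced off-drug count in a descriptive table. No formal hypothesis is tested on the primary safety variables (SAP 4.1).
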